## PROTOCOL SUMMARY:

**Long title:** A Phase 2 Randomized, Double-blinded Trial to Evaluate the Efficacy and Safety of Human Anti- SARS-CoV-2 Plasma for Early Treatment of COVID-19

**Short title:** Convalescent Plasma for Early Treatment of COVID-19

**Clinical Phase:** 2

**IND Sponsor:** [name]

**Principal Investigator:** [name]

**Conducted by:** Columbia University

**Sample Size:** SARS-CoV-2 positive nasal swab at baseline: 150 subjects

**Study Population:** High risk for severe COVID-19 case who are 18 years of age or older and SARS-CoV-2 positive and asymptomatic or mildly to moderately symptomatic at baseline.

**Study Duration:** Accrual will take 4-6 months to complete and subjects will be followed for 90 days after enrollment.

**Study Design:** Double-blinded, randomized control trial to assess the efficacy and safety of anti-SARS-CoV-2 convalescent plasma as early treatment. Participants will be randomized 2:1 to receive either convalescent plasma qualitatively positive for SARS-CoV-2 antibody ("anti-SARS-CoV-2 plasma") or control (albumin 5%).

**Study Locations:** National Institute of Infectious Diseases Evandro Chagas (INI) at Oswaldo Cruz Foundation (Instituto Nacional de Infectologia Evandro Chagas-FIOCRUZ (INI-FIOCRUZ) ([name]); Laboratorio de Pesquisa em DST e AIDS do IPEC/FIOCRUZ (LAPCLIN/AIDS) ([name]); Laboratório Central do Instituto Nacional de Infectologia Evandro Chagas ([name]); Laboratório de Virus Respiratórios e Sarampo (IOC/FIOCRUZ) ([name]); Laboratório Richet de Pesquisa e Fisiopatologia Humana Ltda ([name]); Agência Transfusional - Laboratório Central INI ([name]);

---

 See Section 2.3.1 for definition of high risk

Center for Infection and Immunity ([name]).

**Study Agent:**

- Anti-SARS-CoV-2 plasma: convalescent plasma (2 units of ~200-250 mL, total 400-500 mL) collected by apheresis from a volunteer who recovered from COVID-19 disease (collection and qualification covered by IRB protocol AAAS9845 [Convalescent plasma donors]))
- Control (albumin 5%): 2 units of 250mL, total 500 mL

**Primary Efficacy Objective:**

To evaluate the efficacy of early treatment with anti-SARS-CoV-2 plasma versus control (albumin 5%) at day 28

**Primary Endpoint:** The primary study endpoint will be a rating of disease severity on Day 28, or the last rating evaluated, using a seven-category severity scale:

1. Not hospitalized, negative PCR for SARS-CoV-2
2. Not hospitalized, positive PCR for SARS-CoV-2 without symptoms
3. Not hospitalized, positive PCR for SARS-CoV-2 with symptoms
4. Non-ICU hospitalization, not requiring supplemental oxygen
5. Non-ICU hospitalization, requiring supplemental oxygen
6. Requiring mechanical ventilation and/or in ICU
7. Death

Time to various dichotomizations on the severity scale.

**Primary Safety Objective:** To evaluate the safety of anti- SARS-CoV-2 plasma versus control (albumin 5%)

**Primary Safety Endpoints:**

1. Cumulative incidence of grade 3 and 4 adverse events during the study period
2. Cumulative incidence of serious adverse events during the study period

**Secondary Objectives:**

1. To compare the anti-SARS-CoV-2 titers between the recipients of anti-SARS-CoV-2 plasma versus control (albumin 5%) at days 3, 7, 14, 28 and 90.
2. To compare the proportion and duration of SARS-CoV-2 PCR positivity (RT PCR) between the recipients of the anti-SARS-CoV-2 plasma versus control (albumin 5%) at days 0, 3, 7, 14 and 28
3. To compare the levels of SARS-CoV-2 RNA between the recipients of anti-SARS-CoV-2 plasma and control (albumin 5%) at days 0, 3, 7, 14 and 28

**Exploratory Objective:**

1. To assess the correlation between SARS-CoV-2 PCR positivity from nasal swab specimens, based on RT PCR, and detection of viable SARS-CoV-2 from nasal swab specimens based on viral culture assays

## LIST OF ABBREVIATIONS

ADR: Adverse Drug Reaction  
ADE: Antibody-mediated enhancement of infection  
AE: Adverse Event/Adverse Experience  
CDC: United States Centers for Disease Control and Prevention  
CFR: Code of Federal Regulations  
CLIA: Clinical Laboratory Improvement Amendment of 1988  
COI: Conflict of Interest  
COVID-19: Coronavirus Disease  
CRF: Case Report Form  
DMC: Data Management Center  
DSMB: Data and Safety Monitoring Board  
EUA: Emergency Use Authorization  
FDA: Food and Drug Administration  
GCP: Good Clinical Practice  
HBV: Hepatitis B virus  
HCIP: Human Coronavirus Immune Plasma  
HCV: Hepatitis C virus  
HIV: Human immunodeficiency virus  
HTLV: Human T-cell lymphotropic virus  
IB: Investigator's Brochure  
ICF: Informed Consent (Informed Consent Form)  
ICH: International Conference on Harmonization  
ICU: Intensive Care Unit  
IEC: Independent ethics committee  
IND: Investigational New Drug Application  
IRB: Institutional review board  
ISBT: International Society of Blood Transfusion  
IWRS: Interactive web response system  
MERS: Middle East Respiratory Syndrome  
OP: Oropharyngeal  
RT-PCR: Reverse Transcriptase Polymerase chain reaction  
PK: Pharmacokinetic  
PPE: Personal Protective Equipment  
PTID: Participant ID number  
SAE: Serious adverse event  
SARS: Severe Acute Respiratory Syndrome  
SARS-CoV-2: Severe Acute Respiratory Syndrome Coronavirus 2  
TACO: Transfusion-associated circulatory overload  
*T. cruzi*: *Trypanosoma cruzi*  
TRALI: Transfusion-related acute lung injury  
UP: Unanticipated Problem  
UPnonAE: Unanticipated Problem that is not an Adverse Event  
ZIKV: Zika virus

## 1. BACKGROUND AND SCIENTIFIC RATIONALE

There are currently no proven treatments for mild coronavirus disease (COVID-19) nor are there prophylaxis options for those who have been exposed to the illness, which is caused by Severe Acute Respiratory Syndrome Coronavirus 2 (SARS-CoV-2). Human convalescent plasma has been successfully used for other infection prevention and treatment and thus may provide an option for prevention and treatment of COVID-19 and could be rapidly available from people who have recovered from disease and can donate plasma.

Passive antibody therapy involves the administration of antibodies against a given infectious agent to a susceptible or ill individual for the purpose of preventing or treating an infectious disease caused by that agent. In contrast, active vaccination requires the induction of an immune response that takes time to develop and varies depending on the vaccine recipient. Some immunocompromised patients fail to achieve an adequate immune response. Thus, passive antibody administration, in some instances, represents the only means of providing immediate immunity to susceptible persons and more predictable immunity for highly immunocompromised patients.

Passive antibody therapy has a storied history going back to the 1890s. It was the inaugural form of antimicrobial therapy and the only way to treat certain infectious diseases prior to the development of antimicrobial therapy in the 1940s (Casadevall, Dadachova, & Pirofski, 2004; Casadevall & Scharff, 1995). Experience from prior outbreaks with other coronaviruses, such as SARS-CoV-1 shows that convalescent plasma contains neutralizing antibodies to the relevant virus (Zhang et al., 2005). In the case of SARS-CoV-2, the anticipated mechanism of action by which passive antibody therapy would mediate protection is viral neutralization. However, other mechanisms may be possible, such as antibody dependent cellular cytotoxicity and/or phagocytosis. Convalescent serum was also used in the 2013 African Ebola epidemic. A small 73 non-randomized study in Sierra Leone revealed a significant increase in survival for those 74 treated with convalescent whole blood relative to those who received standard treatment (Sahr et al., 2017).

The only antibody type that is currently available for immediate use is that found in human convalescent plasma. As more individuals contract COVID-19 and recover, the number of potential donors will continue to increase.

A general principle of passive antibody therapy is that it is more effective when used for prophylaxis than for treatment of disease. When used for therapy, antibody is most effective when administered shortly after the onset of symptoms. The reason for temporal variation in efficacy is not well understood but could reflect that passive antibody works by neutralizing the initial inoculum, which is likely to be much smaller than that of established disease. Another explanation is that antibody works by modifying the inflammatory response, which is also easier during the initial immune response, which may be asymptomatic (Casadevall & Pirofski, 2003).

As an example, passive antibody therapy for pneumococcal pneumonia was most effective when administered shortly after the onset of symptoms and there was no benefit if antibody administration was delayed past the third day of disease (Casadevall & Scharff, 1994).

For passive antibody therapy to be effective, a sufficient amount of antibody must be administered. When given to a susceptible person, this antibody will circulate in the blood, reach tissues and provide protection against infection. Depending on the antibody amount and composition, the protection conferred by the transferred immunoglobulin can last from weeks to months.

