## **1.5. SARS-CoV-2 testing**

The Laboratorio de Pesquisa em DST e AIDS do IPEC/FIOCRUZ (LAPCLIN/AIDS), Laboratório de Virus Respiratórios e Sarampo (IOC/FIOCRUZ) or the Center for Infection and Immunity (CII) laboratory will conduct both a quantitative PCR assay and serologic assay. No clinical decisions will be made based on these results.

For asymptomatic individuals, PCR testing alone will be used for screening. For symptomatic individuals, two swabs will be collected from each potential participant, one for ID NOW (or comparable rapid antigen test) and one for a PCR-based test. The ID NOW test results are available in minutes and will make recruitment more efficient. In view of the high specificity of the ID NOW test (99.7%) (Dinnes, et al., 2021), if either the ID NOW and/or the PCR test results is positive, the individual will be confirmed as SARS-CoV-2 positive.

PCR testing will be conducted for all participants at screening, days 0, 3, 7, 14 and 28 and the viral load will be estimated. Results from the baseline ID NOW COVID-19 or PCR tests will be reported to subjects as SARS-CoV-2 positive or negative. Subsequent PCR results will not be shared with the subjects or the clinical research team in order to reduce bias.

ID NOW COVID-19 assay performed on the ID NOW Instrument is a rapid molecular in vitro diagnostic test utilizing an isothermal nucleic acid amplification technology intended for the qualitative detection of nucleic acid from the SARS-CoV-2 viral RNA in direct nasal, nasopharyngeal or throat swabs from individuals who are suspected

of COVID-19 by their healthcare provider within the first seven days of the onset of symptoms. ID NOW COVID-19 received Emergency Use Authorization from the US FDA in September 2020.

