### 2.3.5 Stratified Randomization

1. Subjects enrolled in the study will be stratified and randomized using an interactive web- based system

 Assessment evaluates whether subject has shifted from “no clinical or laboratory evidence of COVID-19 infection to any of the composite outcomes of disease severity

[figure not shown]
 Comprehensive metabolic panel

 Nasal swab

 Includes sequencing for viral variants

 10 % sample of the nasal swabs

2. Subjects will be stratified by steroid administration (prior oral or IV steroids within prior 2 weeks at time of enrollment or prior inhaled steroids within prior 24 hours at time of enrollment) and by vaccination status (prior COVID-19 vaccine at time of enrollment) and then randomized in a 2:1 ratio to either CP or albumin 5%

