## 3.2 Statistical Analysis

Primary Analysis and go/no-go decision: The severity scale of the two groups will be compared using stratified, Mann Whitney test. Specifically, a one-sided  $P < 0.15$  favoring the immune plasma arm will constitute a “go decision” in this phase 2 trial, suggesting evidence of promise for further investigation in an expanded Phase 3 study. The results in this trial will then be used to plan the Phase 3 sample size, with possibility that the data in this Phase 2 trial will be included in the final analysis using adjusted  $P$  values. Details of sample size re-estimation and adjusted analysis, as well as the final statistical analysis plan, will be determined before unblinding the study data.

This analysis will be intent-to-treat. Given the short study duration and the nature of the treatment, however, we anticipate minimal non-compliance and loss to follow-up.

Subgroup Analysis: If the stratified analysis reaches the go decision, with  $P < 0.15$ , we will explore the treatment effect within each stratum using Mann Whitney test.

Secondary Analyses: All secondary efficacy analyses will be intent-to-treat. Time-to-event variables (e.g. time to death) will be analyzed using Cox proportional hazard model. Longitudinal data collected over multiple days (e.g., PCR positivity) will be analyzed using generalized linear mixed models. Treatment effects on these variables will be estimated with 95% confidence intervals.

Safety Analyses: Serious adverse events will be summarized by grades and types using proportions and 95% confidence intervals for the two study arms, and the two arms will be compared using Fisher's exact test.

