### 3.3 Power Consideration

Assuming a shift odds ratio of 2 under a proportional odds model on the severity rating scale, with a sample size of 150, the study will have 74% to 80% power of reaching the go decision in the scenarios we considered. The actual power will depend the distribution of the severity scale in the control arm. Table 2 gives the power of the two extreme scenarios: Scenario 1 describes scenario with higher rates for more severe outcomes, and Scenario 2 with majority of participants remaining or becoming PCR negative; the outcome distributions are identical between the two strata in these scenarios. We have evaluated the power for in-between scenarios and scenarios where non-infected and infected strata are different; the power is within the range 74% and 80% in all scenarios we have considered.

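### The go test leaves screening viral load unused: prespecifying it as a covariate is a nearly free, probably modest gain in power, and an analysis by time since onset should be planned separately

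*Combined protocol and SAP*

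**What the plan says.** Section 3.2 (Statistical Analysis) sets the go test: "The severity scale of the two groups will be compared using stratified, Mann Whitney test". A go needs "one-sided $P < 0.15$ favoring the immune plasma arm". No covariate is named. Section 2.3.5 (Stratified Randomization) gives the factors: "Subjects will be stratified by steroid administration" and by prior COVID-19 vaccination. I read these as the strata of the test, since Section 3.2 lists none.

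Section 1.5 (SARS-CoV-2 testing) says "PCR testing will be conducted for all participants at screening, days 0, 3, 7, 14 and 28 and the viral load will be estimated". A quantitative baseline value is therefore planned for everyone.

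On timing, Section 1 says "When used for therapy, antibody is most effective when administered shortly after the onset of symptoms", and Section 1.1 makes a similar point from the experience with SARS. Eligibility (Section 2.3.1) runs from no symptoms to 7 days of symptoms at screening. Section 3.2 plans subgroup analysis only after a go decision and only within each stratum. It leaves the final analysis plan to be fixed before unblinding.

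On power, Section 3.3 takes 150 participants and a proportional-odds shift with odds ratio 2. Its conclusion is that "the study will have 74% to 80% power of reaching the go decision in the scenarios we considered".

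**The concern.** Categories 1 to 3 of the seven-category scale separate non-hospitalized participants by PCR result and symptoms. A participant's viral load at entry is a natural candidate predictor of whether the Day 28 swab is negative. If it does predict the rating, an unadjusted test treats explainable variation as noise, and the same 150 participants could give somewhat more power at no cost in data.

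A second, separate matter is the argument for treating early. It implies that the treatment effect changes with time since onset, yet no planned analysis looks at this. After a no-go decision no subgroup analysis is planned at all, although a benefit confined to early treatment could itself produce a no-go.

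**Working it through.** **Inputs.** 100 plasma and 50 control participants (Section 3.1); one-sided 0.15 (Section 3.2); odds ratio 2 and the Table 2 control distributions (Section 3.3). The correlation of baseline viral load with the Day 28 rating is not in the documents and is assumed over a range.

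**Step 1: reproduce the stated power.** The Whitehead proportional-odds formula is V = mnN / [3(N+1)²] × (1 − Σp̄³), with power = Φ(ln 2 × √V − 1.036). Here p̄ is the category share averaged over arms at 2:1.

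- Scenario 1: Σp̄³ = 0.480; V = 750,000/68,403 × 0.520 = 5.70; power = Φ(1.655 − 1.036) = 73.2%.
- Scenario 2: Σp̄³ = 0.353; V = 10.96 × 0.647 = 7.09; power = Φ(1.846 − 1.036) = 79.1%.

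Simulation of the tie-corrected Mann-Whitney test (200,000 runs) gives 74.2% with the Table 2 plasma percentages and 75.0% with an exact odds ratio of 2 in Scenario 1, and 80.9% and 80.4% in Scenario 2. Two or four strata of equal risk change this by 0.3 points or less. The stated 74% and 80% stand.

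**Step 2: adjust for a prognostic baseline covariate.** Outcomes come from a latent logistic model with one standard-normal covariate. The marginal odds ratio is held at about 2, with 6,000 runs per case.

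| Scenario | Rank correlation | Unadjusted | Rank ANCOVA | Change (points) |
|---|---|---|---|---|
| 1 | 0 | 74.9% | 74.7% | −0.2 |
| 1 | 0.19 | 74.8% | 75.7% | +0.9 |
| 1 | 0.35 | 76.1% | 79.4% | +3.3 |
| 1 | 0.45 | 76.3% | 82.2% | +5.9 |
| 2 | 0 | 80.8% | 80.6% | −0.2 |
| 2 | 0.21 | 80.4% | 81.4% | +1.0 |
| 2 | 0.38 | 80.1% | 84.5% | +4.4 |
| 2 | 0.49 | 81.6% | 88.8% | +7.2 |

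With no treatment effect, both tests reach a go in 14% to 15% of runs. A separate simulation that added a pure-noise covariate agreed: about 1 point gained at correlation 0.25, 3 at 0.35 and 5 to 6 at 0.42 to 0.46, with at most about 0.6 points lost at zero.

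**Step 3: analytic check.** If adjustment removes a share ρ² of the variance, power = Φ[(1.036 + z)/√(1 − ρ²) − 1.036], where z is the normal quantile of the unadjusted power. From 74%, ρ = 0.2, 0.3, 0.4 and 0.5 give 75.1%, 76.6%, 78.7% and 81.7%. From 80%, they give 81.1%, 82.4%, 84.4% and 87.1%. This is the same pattern as in Step 2. The equivalent gain in sample size is 1/(1 − ρ²): 1.07 at 0.25, 1.14 at 0.35 and 1.27 at 0.46.

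**Step 4: does stratifying on time since onset add power?** Take half early and half late participants with the same control risk, so that timing changes only the treatment effect (200,000 runs).

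| Odds ratio early / late | Scenario | Not stratified on onset | Stratified on onset |
|---|---|---|---|
| 4 / 1 | 1 | 63.3% | 63.6% |
| 4 / 1 | 2 | 70.9% | 71.2% |
| 2 / 1 | 1 | 41.2% | 41.4% |
| 2 / 1 | 2 | 45.1% | 45.3% |

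Stratifying recovers essentially nothing. The 2 / 1 rows show that a real early benefit diluted in this way would more often end in a no-go than a go.

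**Step 5: precision of an analysis by timing.** The standard error of the overall log odds ratio is 1/√V: 1/√5.70 = 0.42 and 1/√7.09 = 0.38. For an early-versus-late half split, the difference of two log odds ratios has about twice that, 2/√V = 0.84 and 0.75. The 95% interval for the ratio of odds ratios then extends by a factor of exp(1.96 × 0.84) = 5.2 or exp(1.96 × 0.75) = 4.3 in each direction.

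**The case against.** The strongest reply is that the planned test is valid, its power is correctly stated, and covariate adjustment is an optional gain whose size nobody can read from the documents. That is right. No section says that baseline viral load predicts the Day 28 rating. Screening swabs may be of two types, may be self-collected, and may be assayed in different laboratories, all of which could weaken the correlation. The simulations compare adjustment with an unstratified Mann-Whitney test, so if steroid use or vaccination is itself prognostic, the increment over the planned test could differ. The final analysis plan is also still open.

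Three stronger readings are tempting, and the documents support none of them.

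- A reader might infer from "When used for therapy, antibody is most effective when administered shortly after the onset of symptoms" that leaving out time since onset costs the go test power. That sentence says that the effect of antibody varies with timing. It does not say that timing predicts outcome regardless of arm, and Step 4 shows that stratifying on a pure effect modifier gains nothing.
- A reader might infer that the outcome is mainly a matter of viral clearance. That fits Scenario 2 of Table 2 (60% against 75% PCR negative). In Scenario 1 no one is PCR negative in either arm, and the contrast is hospitalization or worse (30% against 18%).
- A reader might infer that the trial cannot examine timing. It could; the analysis is just not prespecified.

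Time since onset is also an awkward covariate for the go test. It is undefined for asymptomatic participants and confined to 7 days at screening for the rest. Filling the gap with days since a positive swab would mix two clocks.

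What survives is narrow: a baseline value already planned for everyone is left out of the decision test, and including it costs almost nothing even if it proves uninformative.

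**Conclusion.** The point holds as a low-cost improvement; it does not show an error. Adjusting the go test for screening viral load would add about 0 to 1 point of power at rank correlation 0 to 0.25, about 3 to 4 at about 0.35, and about 5 to 7 at 0.42 to 0.49. If viral load is not prognostic, the loss is under 1 point. The false-go rate remains about 15%. These figures rest on an assumed correlation, a single well-behaved covariate, the Table 2 distributions and a marginal odds ratio of about 2.

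It would be wrong to conclude that the trial is underpowered against its own statement.

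The missing analysis by time since onset is a separate gap. Filling it would let the trial describe the effect that its rationale predicts, with wide intervals, and would not raise the chance of a go.

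**What to change.** Before unblinding, write into the final SAP:

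1. **Go test.** Use the stratified Mann-Whitney test with rank-based covariate adjustment (stratified rank ANCOVA) for screening log10 RNA, at the same one-sided 0.15 threshold. Rank PCR-negative screening swabs lowest. This rule is needed because a footnote to Section 2.3.1 lets some participants with a documented positive PCR in the prior week enroll without a positive screening swab. Keep the unadjusted stratified test as a sensitivity analysis.
2. **Strata.** Name them. Section 3.3 refers to infected and non-infected strata, whereas Section 2.3.5 uses steroid use and vaccination; reconcile the two.
3. **Timing.** Whatever the go decision, report an exploratory treatment odds ratio by days from symptom onset to randomization among symptomatic participants, with asymptomatic participants as their own group and 95% confidence intervals. State that with 150 participants the estimate will be imprecise and that it serves to explain the effect.

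The cost is SAP wording and a little programming. Item 1 needs no new data. For item 3, confirm that the case report form holds an onset date: eligibility requires symptom duration to be checked, but the screening procedures in Section 4.2 do not list the date.
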